The PI will conduct a semiannual assessment of external factors through a review of literature related to new developments in the areas of wound management, pain, exercise and other approaches that may have an impact on the safety of participants or on the ethics of the study.

SECTION F. Interim Analysis

The PM will generate semi-annual qualitative interim analysis reports on data obtained during phone call and returned end-of-study surveys to understand issues related to the uptake, usability, and adoption of this platform among this population. We will evaluate the screening and enrollment procedures, barriers to participation and retention, acceptability, technology problems encountered if any, and user feedback from the participants and providers. This information gained from this structured process will be used to both guide the refinement of the current protocol and to inform the design of a larger efficacy trial. There are no planned stopping rules for this study.

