From the initial screening of participants by inclusion and exclusion criteria to the informed consent process to the provision of participant study instruction to staff training in Good Clinical Practices (GCP) and regulations pertaining to the Conduct of Human Participant Research to weekly contact with participants to internal monthly quality control audits and protocol fidelity monitoring to the real-time review of adverse events (AE) and serious adverse events (SAEs) by the PI, Study Investigators and the ISM, the study will be carefully overseen.

Drs. [name], [name], [name] (Study Statistician), [name], [name], [name] (ISM) [name], [name], [name], and [name] will review the data for this study quarterly. We will examine participant accrual and adherence to the protocol regarding demographics and inclusion and exclusion criteria, and compliance of treatment, AE and SAE rates quarterly, and report regarding statistical power implications of dropouts and missing data annually.

Data on compliance to the intervention will be collected weekly by the Project Manager (PM) and reviewed quarterly by the Study Investigators, Study Statistician, and the ISM. Compliance on the part of participants will be evaluated by attendance and process evaluation as outlined in the study. If intervention attendance drops below 85%, the mothers who have stopped coming will be called to ask for feedback. Using information gained from these phone interviews, the PI will schedule a meeting with the Study Investigators and the ISM to discuss methods for improving compliance.

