[name] (Chairperson of UNC-CH School of Nursing Human Participant Research Review Committee and ISM) will chair the Adverse Event Monitoring Committee, which will include Drs. [name] (PI), [name], [name] (Study Statistician), [name], [name], [name], [name], [name], and [name] and the PM. The committee will meet every 3 months or more often as warranted, to review data related to AEs and SAEs and assure that safety standards are maintained. Despite usual precautions, we are aware that AEs and SAEs may occur, and this committee will monitor their occurrence and the overall risk of the study to both mothers and their children. We will develop a system to test whether abnormalities are equally distributed between the intervention and equal attention control groups. Data will be presented to the committee if a significant increase in abnormalities is noted. The committee will be asked to establish measurable standards that must be met before they recommend modification of the study on the basis of safety. These standards will be clearly delineated in the meeting minutes and approved by the committee. The committee will provide the PI with recommendations regarding problems that would require modification for safety reasons. Minutes of each meeting will be kept, and all actions and decisions documented to establish an audit trail. [name], the Study Statistician, will be instructed by the PI to prepare the randomization plan for the study and prepare reports for the committee under the direction of [name] (Chair and ISM).

2) Reviewing. Adverse events will be assessed and graded as follows.

Expected/Anticipated—Identified in nature, severity, or frequency in the current protocol, informed consent, investigator brochure, or with other current risk information.

Unexpected/Unanticipated—Not identified in nature, severity, or frequency in the current protocol, informed consent, investigator brochure, or with other current risk information.

More Prevalent—Occurs more frequently than anticipated or at a higher prevalence than expected.

Serious—Results in death, is life threatening, requires inpatient hospitalization or prolongs existing hospitalization, results in persistent or significant disability/incapacity, cancer, overdose, or causes a congenital anomaly/birth defect.

The relationship of AE to study participation will be determined by the Adverse Monitoring Committee as follows.

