Unrelated—There is not a reasonable possibility that the adverse event may have been caused by the drug, device or intervention.

Possibly Related—The adverse event may have been caused by the drug, device, or intervention, however there is insufficient information to determine the likelihood of this possibility.

Related—There is a reasonable possibility that the adverse event may have been caused by the drug, device or intervention.

3) Reporting. The PI will responsible for ensuring that all AE and SAEs are reported to the NIH/NINR ([name]) and UNC-CH's IRB in compliance with their requirements.

Any AE will be reported by the PI to the Adverse Event Monitoring Committee within one week. An incident report will be created and sent by electronic email by the PI to Drs. [name], [name] (Study Staistician), [name], [name], [name] (ISM) [name], [name], [name], and the PM. The PI will follow-up with the mother and child and will prepare a report. The AEs will be reviewed every three months and a report prepared for the Human Participants Committee and [name] at NIH/NINR. Process notes will be kept concerning any decisions.

Any SAE or deaths that occur during the study will be reported by telephone immediately to the Human Participants Research Review Committee Chairperson and [name] (ISM) and to NIH/NINR ([name]). An incident report will be sent by electronic mail by the PI to Drs. [name], [name], [name], [name], [name], [name], [name], and the PM. The PI will follow-up immediately with the mother and child to investigate and prepare a report for all members of the Human Participants Committee and comply with all regulations regarding the reporting of SAEs. If the PI is unavailable, [name] will be on-call in the PI's absence. The PI or [name] in the PI's absence will be responsible for complying with all regulations concerning the reporting of a SAE and will prepare a full report for NIH/NINR. It is not expected that the committee will be involved in the decision to terminate the intervention for a study participant related to any adverse event. The PI will meet with the Study Investigators and the PM and seek input from the Program Officer ([name]) and [name] (ISM). Process notes will be kept concerning any decisions.

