4) Examples of Potential Reportable Adverse Events. An AE is reportable if it meets all of the following criteria: 1) is unexpected 2) is related and/or possibly related, and 3) is serious and/or suggests that the research places subjects or others at a greater risk of physical or psychological harm than was previously known or recognized. Additionally, per UNC-CH's policy all participant deaths, protocol deviations, complaints about the research, and breaches of confidentiality are reportable events.

An example of an AE would be that a 3-5-year old child decreases from the 25th percentile (normal or healthy weight) to below the 5th percentile (underweight) at the next data collection. The steps to be taken include withdrawing the child and their mother from the study. The PI will immediately contact [name] (Pediatrician), [name] (ISM), the IRB Contact person, and Program Officer [name] at NIH/NINR. The PI will assist the mother to call her Pediatrician and set up an immediate appointment to have her 4-year old child evaluated and ensure that follow-up was received.

An example of an SAE would be the death of a participant from acute renal failure, which although would be viewed as unexpected and unrelated to the intervention is nonetheless a reportable serious event. No further steps would be taken except to review, grade and report the event.

5) Safety Review Plan. Study progress and safety will be reviewed monthly (and more frequently if needed). Progress reports, including participant recruitment, retention/attrition, and AEs will be provided to [name] (ISM) following each of the monthly reviews. An annual report will be compiled and will include a list and summary of AEs and SAEs. In addition, the annual report will address (1) whether adverse event rates are consistent with pre-study assumptions; (2) reason for dropouts from the study; (3) whether all participants met entry criteria; (4) whether continuation of the study is justified on the basis that additional data are needed to accomplish the stated aims of the study; and (5) conditions whereby the study might be terminated prematurely. The annual report will be signed by [name] (ISM) and will be forwarded to the IRB and NIH/NINR. The IRB will review progress of this study on an annual basis.

SECTION D. Multi-Site Monitoring and Compliance

This is not a multi-site study.

SECTION E. Assessment of External Factors

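### The only planned between-arm comparison of safety events goes to the monitoring committee on an undefined significance trigger, and no by-arm table is promised otherwise

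*Combined protocol and SAP*

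**What the plan says.** The rule stands in two consecutive sentences of DSMP Section C, item 1. The first reads "We will develop a system to test whether abnormalities are equally distributed between the intervention and equal attention control groups". The second reads "Data will be presented to the committee if a significant increase in abnormalities is noted". The plan gives no test, significance level, sidedness, unit of analysis or testing schedule, and does not say which events count as abnormalities.

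Four other routes carry safety data without a condition:

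- Section C, item 1: "The committee will meet every 3 months or more often as warranted, to review data related to AEs and SAEs".
- Section C, item 3: "Any AE will be reported by the PI to the Adverse Event Monitoring Committee within one week".
- Section B, item 1: the investigators, statistician and independent monitor examine "compliance of treatment, AE and SAE rates quarterly".
- Section C, item 5: "Progress reports, including participant recruitment, retention/attrition, and AEs will be provided to" the independent monitor after each monthly review.

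None of the four says that the data are split by arm. Thresholds for action are deferred: "The committee will be asked to establish measurable standards that must be met before they recommend modification of the study on the basis of safety". Protocol section 9.4.4 (Safety Analyses) is a heading with no text of its own, section 8.2 is marked not applicable, and DSMP Section F says that no stopping rules are planned.

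**The concern.** A safety committee compares arms in order to see imbalances that single case reports do not show. Here the one comparison by arm in the DSMP is presented on condition of a significant result. Significance is a poor filter for uncommon events in a trial of this size, because an imbalance that the committee would want to discuss can easily fall short of it. The committee must also set its own standards for modifying the study, and it is not assured of by-arm data when it does so.

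**Working it through.** **Inputs from the documents.** Section 9.2 enrols 294 dyads, 147 per group, for 250 completers after 15% attrition. This reproduces: 250 / 0.85 = 294.1. Section 5 enrols in eight cohorts over four years, so many quarterly meetings come with far fewer than 147 per arm. The plan states no power or rate for the safety trigger, so there is no figure of its own to reproduce.

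**Assumptions.** The test is two-sided at 0.05 (borrowed from the efficacy calculation in section 9.2), the unit is the dyad, there is one look, and control rates run from 1% to 10%.

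**Pooled two-proportion test.** Power = Φ{[d√n − 1.96√(2p̄(1−p̄))] / √(p₁(1−p₁) + p₂(1−p₂))}, where d = p₂ − p₁ and p̄ is the mean of the two rates.

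For 5% v 10% with n = 147:

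- d√n = 0.05 × 12.124 = 0.606
- 1.96 × √(2 × 0.075 × 0.925) = 0.730
- denominator √(0.0475 + 0.0900) = 0.371
- power = Φ(−0.334) = 0.37

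**Fisher's exact test.** Power is the sum of the binomial probabilities of all count pairs with a two-sided p below 0.05.

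| Control v intervention | Per arm | Pooled | Fisher |
|---|---|---|---|
| 1% v 3% | 147 | 0.23 | 0.09 |
| 2% v 4% | 147 | 0.17 | 0.09 |
| 2% v 6% | 147 | 0.42 | 0.30 |
| 3% v 9% | 147 | 0.58 | 0.49 |
| 5% v 10% | 147 | 0.37 | 0.29 |
| 5% v 15% | 147 | 0.82 | 0.79 |
| 10% v 20% | 147 | 0.67 | 0.62 |
| 2% v 6% | 74 | 0.24 | 0.09 |
| 5% v 10% | 74 | 0.21 | 0.13 |
| 5% v 15% | 74 | 0.53 | 0.44 |

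**Control rate at which pooled power is 50%.** Below this rate, the increase is missed more often than not.

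| Per arm | Doubling | Tripling |
|---|---|---|
| 147 | 7.0% | 2.5% |
| 74 | 12.6% | 4.7% |
| 37 | 21.2% | 8.6% |

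**In counts at 147 per arm (two-sided Fisher).** Splits of 5 v 0 (p = 0.060), 7 v 1 (p = 0.067) and 9 v 2 (p = 0.061) are not significant. It takes 6 v 0, 8 v 1 or 10 v 2 to cross 0.05.

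**Sensitivity to the assumptions.** A one-sided 5% pooled test raises 5% v 10% to 0.49 and 3% v 9% to 0.70. If mothers and children are counted separately and treated as independent (294 per arm), the 50% points fall to about 3.7% for a doubling and 1.3% for a tripling. Repeated uncorrected looks would raise both detection and false alarms. The plan gives no testing schedule, so they are not modelled here.

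**The case against.** A reader might infer that the committee sees adverse-event data only after a significant result. The documents do not support that. The word *only* is not in the sentence, every event goes to the committee within a week, and the committee reviews event data every three months. The sentence can be read as an added escalation step.

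Nor do the documents show that the committee would be unaware of arm:

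- An injury in a study exercise class reveals the arm by itself, since control mothers attend English classes.
- A child's fall to below the 5th BMI percentile is the DSMP's own adverse-event example and prompts immediate contact with the monitor.
- The committee judges how each event relates to participation.
- Blinding is stated only for the data-collection assistants (section 6.3), and the statistician and project manager are committee members.

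A reader might also infer that the trigger would usually miss any doubling or tripling. That is too strong. It rests on rates, a test and a level that the plan does not give, and it fails at full enrolment for a tripling from 5% or a doubling from 10%.

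Finally, the DSMP rates the study as no more than minimum risk and expects no adverse effects. This limits how much is at stake. It also makes low event rates the likely case, and there the trigger is weakest.

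All of this narrows the point. What remains is that no route promises a cumulative comparison by arm. Knowing the arm of single events is not the same as seeing counts and denominators side by side, so the text needs changing under either reading of the sentence.

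**Conclusion.** The point holds in a limited form. The DSMP ties presentation of its between-arm comparison to an undefined significant increase, and no other section assures by-arm safety data. Individual events and overall data do reach the committee unconditionally, and no event is shown to go unreported.

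Under the assumed two-sided 5% test per dyad, one look at 147 per arm misses most doublings from control rates below about 7% and most triplings from below about 2.5%. Fisher's test is weaker. Larger increases in commoner events would usually be found at full enrolment, and less often at earlier looks. The lack of definition and of a routine table is plain from the text. The power figures depend on the assumed rates, test, unit and look size. This is an inexpensive improvement to safety reporting.

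**What to change.** In DSMP Section C, item 1, replace the conditional sentence with wording such as: *At every three-monthly meeting the statistician gives the committee chair (the independent monitor) cumulative adverse and serious adverse event counts and rates by arm, with denominators, the rate difference and its 95% interval, regardless of statistical significance.* State whether mothers and children are tabulated separately, and define abnormalities if the term is kept. If a test is also kept, name it and its level, and say that it adds to the table and is not a condition for showing it.

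The cost is one standing table from the statistician, who already prepares the committee's reports under the chair's direction. The small downside is that by-arm data need closed handling, because the principal investigator and project manager sit on the committee. The change adds no stopping rule and leaves clinical management as it is.

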8.3.3.3 EXPECTEDNESS

N/A

8.3.4 TIME PERIOD AND FREQUENCY FOR EVENT ASSESSMENT AND FOLLOW-UP

See DSMP above for detail

8.3.5 ADVERSE EVENT REPORTING

See DSMP above for detail

8.3.6 SERIOUS ADVERSE EVENT REPORTING

See DSMP above for detail

8.3.7 REPORTING EVENTS TO PARTICIPANTS

See DSMP above for detail

8.3.8 EVENTS OF SPECIAL INTEREST

N/A

8.3.9 REPORTING OF PREGNANCY

If a woman becomes pregnant while she is in the study she will be withdrawn and follow-up ensured with her obstetric health care provider.

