4.4 END-OF-STUDY DEFINITION

A participant is considered to have completed the study if she and her child has completed Time 1 (baseline), Time 2 (9 months) and Time 3 (15 months) data collection.

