5.2 EXCLUSION CRITERIA

Health care providers will not be asked to give permission for mother-child dyads to join the study. Mothers will fill out a health history questionnaire to ascertain if they have a heart murmur, congenital heart disease, family history of sudden death, difficulty exercising or psychological problems that would prevent participation. A sports physical will be conducted by a bilingual nurse practitioner on all mothers during baseline data collection to ensure that they have no medical problems. If a mother answers yes to any of these health history questions or the nurse practitioner finds a heart murmur or any other concerns, she will be excluded from the study and referred to a health care provider.

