Weight management studies typically have attrition rates ranging from 10%-30% [19]. To strengthen retention, our classes will be interactive, with culturally and linguistically tailored content developed to engage and sustain the interest of the mother-child dyads. Mothers who miss class will be offered a make-up class over the phone, and reminded when the next class will be held. Additional incentives will include childcare for other children who accompany mothers and their 3-5-year-olds to class and recipes and handouts in Spanish on how to improve their children's nutrition and physical activity behaviors. Mothers will be asked for telephone numbers of several family members and permission to call them if we cannot reach them. We will be as flexible as possible in scheduling enrollment and data collection appointments and provide tokens of appreciation such as birthday cards and a quarterly newsletter with updates on the study. Mothers in both groups will receive \$25 after each data collection. These approaches proved successful in our pilot study with Hispanic mothers with limited English proficiency, where attrition was only 9%-15% [23] and those mothers who stopped coming had moved out of the state. We will make every effort to keep our attrition rate lower than the projected 15%. If retention rates drop below 85%, we will contact the mothers to ask why they stopped coming and develop strategies to meet the needs of each mother to assist them to continue in the study if possible.

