9.3 POPULATIONS FOR ANALYSES

Means, standard deviations, minimums, medians, and maximums will be determined for each continuous variable; frequencies and percentages will be tabulated for each categorical variable. Preliminary analyses will be performed to determine whether, despite randomization, the intervention and control groups were unbalanced on gender, age, or income. Any variable with an imbalance between the groups at baseline will be examined to determine whether it is related to any of the outcome variables. If significant relationships are identified, the variable will be included as a covariate in the models for the affected outcome(s) as a potential confounder. An intent-to-treat analysis will be used in which all subjects are included in the analysis and analyzed according to their initial randomized assignment.

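### Withdrawal for pregnancy makes no provision for further data collection and leaves the child's follow-up undefined, and pregnancy at baseline is not a named criterion

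*Combined protocol and SAP*

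**What the plan says.** Section 8.3.9 is the only rule on pregnancy: "If a woman becomes pregnant while she is in the study she will be withdrawn", with her care followed up by her obstetric provider. It is silent on the child and on whether any remaining assessments of either person are still made.

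The surrounding sections work by dyad. Section 6.3 randomises dyads. Section 4.4 counts a participant as having completed the study "if she and her child has completed Time 1 (baseline), Time 2 (9 months) and Time 3 (15 months) data collection". The schedule of activities (1.3, repeated in 8.1) makes the mother the respondent for her own questionnaires and for the food recall and accelerometer data of both. Section 2.3.1 has the child measured with the mother present. Section 7.2 does not replace participants who withdraw after receiving the intervention.

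On analysis, Section 9.3 promises intent-to-treat, in which "all subjects are included in the analysis and analyzed according to their initial randomized assignment". Section 9.4.10 bases the primary analyses on whatever data are available and keeps imputation as a sensitivity analysis, used if missingness differs by group.

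On entry, Section 5.1 has no criterion on pregnancy. The health history items in Section 5.2 are "heart murmur, congenital heart disease, family history of sudden death, difficulty exercising or psychological problems". The same section lets the nurse practitioner exclude a mother for other concerns found at the sports physical, without naming pregnancy.

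**The concern.** New pregnancies are foreseeable among mothers of 3-5-year-olds followed for 15 months. The rule does not separate two things: what happens to the mother's participation, and whether outcomes are still measured. With no provision for measurement after withdrawal, her self-efficacy and health behaviour data at the remaining visits are lost to Aim 2. The child's later visits depend on how staff read the rule.

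The child's measures matter most. BMI percentile, waist and skinfolds are the Aim 1 primary outcomes, and the mother's pregnancy does not invalidate them. If they are not collected, the loss was avoidable, and no analysis of available data can recover it.

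Entry is a separate gap. A mother already pregnant at Time 1 is not covered by 8.3.9, which concerns a pregnancy that begins during the study. If she is not excluded at the sports physical, a BMI taken in pregnancy can decide her eligibility and her stratum (6.3) and her category in the exploratory aim. Time 1 is one of the modelled outcome occasions, so that BMI and waist also enter the time-by-group contrast in Aim 2.

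**Working it through.** **1. What the text settles.**

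| Question | Where | Answer in the text |
|---|---|---|
| Is the mother withdrawn? | 8.3.9 | Yes |
| Are her later measures collected? | 8.3.9, 7.2 | No provision |
| Is the child withdrawn? | 8.3.9 | Not stated |
| Can the child count as a completer alone? | 4.4 | No; completion is joint |
| Do measures already taken stay in? | 9.4.10 | Yes |
| Is pregnancy at entry a named criterion? | 5.1, 5.2 | No; discretionary screen only |

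**2. The plan's own figures (Section 9.2).** Enrolment: 250 / 0.85 = 294.1, and 294 × 0.85 = 249.9, which agrees with 294 enrolled and 250 completing.

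For power I took three time points, compound symmetry with correlation ρ, and the same standardised difference d at Time 2 and Time 3. The two-degree-of-freedom interaction test then has noncentrality λ = n d² / [3(1 − ρ)], with n per group, and an F reference with 2 and 2n − 3 degrees of freedom. At n = 125:

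- Child BMI percentile (d = .59, ρ = .30): λ = 125 × .3481 / 2.10 = 20.7, power 98.7% (stated above 95%).
- Mothers' BMI (d = .53, ρ = .25): λ = 125 × .2809 / 2.25 = 15.6, power 95.0% (stated above 95%; agrees to rounding).
- Lower scenario (d = .45, ρ = .20): λ = 125 × .2025 / 2.40 = 10.5, power 83.2% (stated above 80%).

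The plan does not state its mean pattern. A difference that grows linearly to Time 3 gives 94.9%, 87.1% and 70.7%, so the agreement depends on the sustained pattern assumed here.

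**3. Size of the loss.** The documents give no pregnancy rate. Assume that 5-10% of the expected completers are lost in addition:

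- 5%: 250 × 0.95 = 237.5 completers; standard error ratio √(250 / 237.5) = 1.03.
- 10%: 250 × 0.90 = 225 completers; standard error ratio √(250 / 225) = 1.05.

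**4. Power under a slightly harsher version.** Here the extra loss is 5 or 10 percentage points of the 294 enrolled: 294 × 0.80 = 235.2 and 294 × 0.75 = 220.5 dyads.

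| Extra loss | Dyads | Child, pilot values | Lower scenario |
|---|---|---|---|
| 0 | 250 | 98.7% | 83.2% |
| 5 points | 235 | 98.2% | 80.7% |
| 10 points | 220 | 97.5% | 77.9% |

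Every lost dyad is treated as contributing nothing. Under the planned mixed model it would still contribute its earlier measures, so these figures overstate the harm at each assumed rate.

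**The case against.** A reader might infer that a mother's pregnancy ends the dyad's follow-up and removes the child's Aim 1 outcomes. The documents do not say so. Section 8.3.9 speaks only of the woman. Section 4.4 defines completion; it is neither a withdrawal rule nor an analysis set. Where joint withdrawal is meant, the safety monitoring plan under 8.3.3.2 names both members, in its example of a child who becomes underweight: "The steps to be taken include withdrawing the child and their mother from the study". Even if the child's visits did stop, baseline and any Time 2 data already collected would remain in the models.

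Nor do the documents support reading this as a breach of intent-to-treat, since a child with partial data is still analysed as randomised. The entry point is not a contradiction either: one rule covers pregnancy arising during the study, pregnancy at entry is not named, and the sports physical may catch it. The health history form is not reproduced and may already ask.

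On size, the 15% attrition allowance is not broken down by cause, so some pregnancies may already be inside it. The remark in Section 5.5 that "those mothers who stopped coming had moved out of the state" describes the pilot, whereas Section 9.2 cites two sources for its attrition range. Nothing in the documents suggests that pregnancy differs by arm, so the expected cost is lost precision and added noise, with no argued bias.

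All of this stands. The gap remains: no passage provides for measurement after withdrawal, the child's status has to be guessed, and under 4.4 the child cannot count as a completer once the mother has left.

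**Conclusion.** The point holds as a gap in data collection rules. As written, the mother's remaining data stop, the child's later Aim 1 measures are left undefined and plausibly lost, and pregnancy at Time 1 is left to discretion.

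The cost is modest. At an assumed 5-10% additional loss there would be about 225-237 completers instead of 250 and a standard error about 3-5% larger. That is an upper bound at those rates, because partial data count and the attrition allowance may already include some pregnancies. Child power at pilot values stays above 95% in the check; only the plan's lower scenario crosses its 80% mark, between 5 and 10 points of extra loss. The size of any distortion from maternal measures taken in pregnancy cannot be derived from the documents. The case for acting is that the child's loss is avoidable and cheap to prevent.

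**What to change.** Leave any decision about classes or clinical care as it is, and separate it from measurement:

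- **8.3.9:** state that withdrawal for pregnancy does not end data collection. The child remains in Time 2 and Time 3 measurement and in Aim 1. The mother's non-anthropometric measures continue to be collected for Aim 2.
- **9.4.10:** prespecify how maternal BMI, waist and skinfolds affected by pregnancy are handled, at Time 1 as well as at follow-up, and whether this extends to measures soon after delivery.
- **4.4:** define completion separately for mother and child.
- **Health history forms (Time 1 questionnaire; Time 2 and Time 3 updates):** record pregnancy status at each time point, if they do not already.
- **5.1/5.2 and 8.3.9:** reconcile them so that the handling of pregnancy at entry is explicit. Which entry rule to adopt is for the investigators.

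The cost is a few sentences, one item on forms already in use, and up to two data collection visits retained for each affected dyad.
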